9.5 Statistical Analyses

9.5.1 Analysis Populations

The following analysis population will be defined for the study:

- Intent-to-Diagnose (ITD) Population Subjects who are enrolled in the study, administered Tc 99m tilmanocept and unfiltered Tc 99m sulfur colloid, and are imaged will be included in the ITD analysis population.
- Safety Population All patients who are enrolled and administered Tc 99m tilmanocept and unfiltered Tc 99m sulfur colloid in the study will be included in the safety population.

All safety data analyses will be conducted on the safety population. All efficacy data analyses will be conducted on the ITD population.

9.5.2 Analysis of Baseline and Demographic Characteristics

The distribution of each baseline and demographic variable of interest will be summarized by dose group. Continuous variables will be summarized via mean, median, standard deviation, and range. Categorical variables will be summarized via counts and percentages.

9.5.3 Analysis of Efficacy Variables

Co-location of tilmanocept and sulfur colloid intrahepatic tessellation localization (Figure 7) will be assessed through frequency tables derived by creating virtual slices of the liver.. These scans will be false-colored and overlaid, matching landmarks (e.g. large blood vessels) for image registration. The resulting voxel colors will be classified as binding tilamanocept, binding sulfur colloid, or binding both. No formal hypothesis tests are planned. Frequency tables will created for individual subjects and overall.

The voxel radiation intensities will be used to create non-parametric density estimates of ^{99m}Tc gamma radiation intensities for both Tc 99m tilmanocept and Tc 99m sulfur colloid. Density estimates will be created for both individual subjects and for NASH subjects and healthy controls pooled separately.

[figure not shown]

Figure 7. Diagrmatic representation of anticipated tessellation

Complete analyses and details will be described in the Statistical Analysis Plan (SAP) for the study.

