	Concordance of intrahepatic localization tessellation discrimination of Tc 99m sulfur colloid (intrahepatic disease heterogeneity) by SPECT/CT imaging and elastography	
Data Analyses	The following analysis population will be defined for the study:	
	• Intent-to-Diagnose (ITD) Population - Subjects who are enrolled in the study, administered Tc 99m tilmanocept and unfiltered Tc 99m sulfur colloid, and are imaged will be included in the ITD analysis population.	
	• Safety Population – All patients who are enrolled and administered Tc 99m tilmanocept and unfiltered Tc 99m sulfur colloid in the study will be included in the safety population.	
	All safety data analyses will be conducted on the safety population. All efficacy data analyses will be conducted on the ITD population.	
	The number and percentage of subjects experiencing noxious pharmacologic activity or ADRs will be tabulated by subject type, Tc 99m tilmanocept dose group (if applicable), and overall.	

Confidential Page 12 of 71

Tc 99m tilmanocept Clinical Study Protocol Number: NAV3-30

> Per subject localization rates and percentage will be calculated by time point, by subject type, Tc 99m tilmanocept dose group (if applicable), and overall.

> Localization intensities (tessellation) will be summarized by descriptive statistics (mean, median, standard deviation, minimum, maximum and range) at each time point. All results will be compared to statistics computed on the control group at each time point.

Confidential Page 13 of 71

Clinical Study Protocol Number: NAV3-30

LIST OF ABBREVIATIONS AND DEFINITIONS OF TERMS

ADR adverse drug reaction

AE adverse event

ALT alanine aminotransferase (SGPT)

AST aspartate aminotransferase (SGOT)

[figure not shown]
BMI body mass index

BUN blood urea nitrogen

CCL2 CC-chemokine ligand 2

CCR2 CC-chemokine receptor 2

CD206 Mannose-binding receptor (Ca2+-binding lectin)

CO₂ carbon dioxide

CRA clinical research associate

CRF case report form

CRO contract research organization

CSF1 Macrophage colony-stimulating factor 1

CSF1R CSF1 receptor

CT X-ray computed tomography

CX3CR1 CX3C-chemokine receptor 1

CXCL CXC-chemokine ligand

CXCR CXC-chemokine receptor

Clinical Study Protocol Number: NAV3-30

Cy3 cyanine dyes fluoresce orange (~550 nm excitation, ~570 nm

emission)

$$\begin{array}{c|c} & 1 & 3 \\ & & 1 \\ \hline & 1 \\ & & R \\ & & Cy3 \end{array}$$

DAMPs Damage-associated molecular patterns

DICOM Digital Imaging Communications in Medicine

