8.2 SPECT/SPECT-CT Image Acquisition

The camera used to obtain the images should be a dual-headed SPECT or SPECT/CT camera equipped with a low-energy, high-resolution collimator with a 15% window (20% can be used if 15% setting not available) centered over a 140keV peak.

The camera must have passed the daily SPECT QC tests as per the manufacturer's recommendation for that day's scan schedule.

Whenever possible, subjects should be asked to void after injection and prior to the first imaging session and again between imaging sessions.

Subjects should be positioned supine with arms at their side. The subject's head, legs, hands, and hips should be in the true anterior position. The subject should be instructed to remain as motionless as possible during the scan, and asked to breathe as shallowly as comfortable when the camera is passing over the chest. To help minimize leg motion, a light taping around the ankles can be used to keep the legs together. A pillow under the knees is often very helpful for comfort.

A planar scan of the liver followed by SPECT/CT should be obtained at the following time points following administration of the specified product:

Unfiltered Tc 99m Sulfur Colloid:

• 20 ± 5 minutes post administration

Tc 99m Tilmanocept:

- 20 ± 5 minutes post administration
- 75 ± 15 minutes post administration
- 180 ± 15 minutes post administration

It is anticipated that the planar scan would be acquired for 25-30 minutes. Using state-of-the-art 2-headed cameras (nominal 20" x 15" FOV), a target of 5-7 million counts should be obtained for the summed view of both heads. For higher activity injections, it may be possible to attain this target in a shorter time, allowing the subject more time off the bed between scans. A simple measure of the subject's "thickness" (i.e. from a lateral visual view, the height of the subject's anterior-most chest/abdomen above the scan bed) should be documented. This will be used for the attenuation correction to be applied to the anterior/posterior views obtained from the planar scan.

Following completion of the planar imaging session at the designated time points, a 3D SPECT/CT should be obtained on the liver, spleen, and abdomen, followed by a patient break.

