It is anticipated that each planar or SPECT/CT scan would be acquired for 25-30 minutes (30 minutes preferred). A break between scans should address the comfort of the patient, encouraging the subject to void, consume fluids or food and to move or rest freely. It is very important that the subject remain motionless for the duration of each scan.

The SPECT transverse slices will be reconstructed using the manufacturer's recommended reconstruction algorithms including the recommended attenuation correction.

It is strongly recommended that each site should perform all imaging acquisitions per their camera manufacturer and model parameters and in accordance with their institutional practices for both the planar imaging as well as the SPECT/CT imaging acquisitions.

De-identified DICOM (Digital Imaging Communications in Medicine) copies of all acquired images will be transmitted to Navidea Biopharmaceuticals. The areas of localization will be identified, documented and captured in the CRFs.

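### The tilmanocept/sulfur colloid co-location table has no reference for the discordance that noise and misregistration produce by themselves; the scheduled repeat tilmanocept scans can supply an approximate one

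*Combined protocol and SAP*

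**What the plan says.** The third secondary objective (Section 2.2) compares the liver distribution patterns of the two agents. Section 9.5.3 does this by voxel overlay: "These scans will be false-colored and overlaid, matching landmarks (e.g. large blood vessels) for image registration". It continues: "The resulting voxel colors will be classified as binding tilamanocept, binding sulfur colloid, or binding both". The reporting is descriptive: "No formal hypothesis tests are planned", and "Frequency tables will created for individual subjects and overall".

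The section gives no positivity threshold, no class for voxels positive on neither scan, no registration tolerance or error measure, and no table for two scans of the same agent. It does not say which tilmanocept scan is overlaid. Under Section 8.2, sulfur colloid is imaged once, at "20 ± 5 minutes post administration". Tilmanocept is imaged at that time point and again at 75 ± 15 and 180 ± 15 minutes.

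The only reference comparison is in the Synopsis, under Data Analyses: "All results will be compared to statistics computed on the control group at each time point". Section 9.5.3 leaves the rest to a later document: "Complete analyses and details will be described in the Statistical Analysis Plan (SAP) for the study".

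**The concern.** The two scans are three days apart and are aligned by landmarks. If the agents had exactly the same distribution, independent count noise would still push some voxels above the cut on one scan and below it on the other, and residual misalignment would do the same. Both single-agent classes would fill, and the plan's label for them is binding.

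This matters because Section 1.3 predicts that colloid penetrates the liver poorly and misses macrophage aggregates that tilmanocept can reach. A count of tilmanocept-only voxels is the pattern that prediction leads one to expect. Without a same-agent figure beside it, nobody can tell how much of the count is technical. The third secondary objective would then be answered by a table that has no scale.

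**Working it through.** **Inputs from the documents.** Scan times as above; planar and SPECT/CT acquisitions of 25–30 minutes each (Section 8.2); 8.0 mCi sulfur colloid and 8.0 or 2.5 mCi tilmanocept (Section 5.2); half-life 6.02 h (Section 1.4.3). The plan gives no expected value for the co-location table, so there is no stated figure to reproduce.

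**Inputs not in the documents (assumptions).** Counts per voxel, true uptake CV, threshold, shift and uptake texture.

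**Step 1: noise only, perfect registration, identical true uptake.** Let mean counts be c and true uptake CV be v. Two independent Poisson images of one map correlate at ρ = c·v²/(1 + c·v²). With a median cut on each image and a normal approximation, the fraction positive on both is B = 1/4 + arcsin(ρ)/(2π). The discordant share of positive voxels is (1 − 2B)/(1 − B).

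- c = 50, v = 10%: ρ = 0.5/1.5 = 0.333, B = 0.304, share = 0.392/0.696 = 56%.
- c = 200, v = 20%: ρ = 8/9 = 0.889, B = 0.424, share = 0.152/0.576 = 26%.
- c = 500, v = 30%: ρ = 45/46 = 0.978, B = 0.467, share = 0.066/0.533 = 12%.

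Direct Poisson simulation agrees. Ranges within a cell reflect how tied counts at the cut are handled:

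| Counts per voxel | CV | Lower-quartile cut | Median cut |
|---|---|---|---|
| 50 | 10% | 31–35% | 55–59% |
| 50 | 30% | 17–18% | 32–34% |
| 200 | 10% | 23–24% | 42–43% |
| 200 | 20% | 14% | 26–27% |
| 400 | 30% | 7% | 14% |
| 500 | 10% | 17–18% | 31–32% |
| 500 | 30% | 6% | 12% |

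The span is 6–59%. The threshold alone roughly doubles the figure in most rows, so a threshold must be fixed before either table means anything.

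**Step 2: adding a shift.** This was a 3D simulation with identical true uptake. Assumed: 4.8 mm voxels, 1.37 L ellipsoid liver, uptake texture 15 mm FWHM, noise 10 mm FWHM, uptake CV 10–20%, median cut. Discordant share of positive voxels:

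- no noise, no shift: 0%
- noise 5–10%, no shift: 20–50%
- shift 5–10 mm, no noise: 34–52%
- both: 38–60%

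**Step 3: carry-over and decay.** Sulfur colloid activity left at 72 h is 0.5^(72/6.02) = 0.025%, so carry-over is not a cause. Between tilmanocept scans, 0.5^(0.917/6.02) = 90% of activity remains from 20 to 75 minutes and 0.5^(2.667/6.02) = 74% from 20 to 180 minutes. The added noise raises discordance by about one percentage point.

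**Step 4: how good is a same-agent reference?** With CV 20%, noise 5% and a median cut, the 20/75 pair gives 20%, 30% and 38% discordance at 0, 2.5 and 5 mm shift; the 20/180 pair gives 21%, 31% and 39%. Two different agents with identical uptake give 38% at 5 mm and 53% at 10 mm. The reference therefore matches the floor only if the registration error is the same. With 2.5 mm error within a day and 10 mm between days, subtraction would leave 53 − 30 = 23 points of apparent difference between identical agents.

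The bias can also run the other way. True maps correlated at 0.9 instead of 1 raise the share from 38% to 43% at 5 mm, so tilmanocept redistribution between its own scans would inflate the reference. At 2.5 mCi, noise is √(8.0/2.5) = 1.79 times higher. The floor for 8.0 mCi colloid against 2.5 mCi tilmanocept is then 42%, against 39% when both are 8.0 mCi, and the 2.5 mCi same-agent figure is 44%.

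**Step 5: timing of the 20/75 pair.** If acquisition starts at 15–25 minutes and takes two scans of 25–30 minutes, it ends between 15 + 50 = 65 and 25 + 60 = 85 minutes. The next window is 60–90 minutes. The two sessions may be nearly back to back, with little of the break that Section 8.2 describes as "encouraging the subject to void, consume fluids or food and to move or rest freely". This pair has the least kinetic change but also the least repositioning.

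**The case against.** The strongest reply is that this is a Phase 1 feasibility study of up to 12 subjects with a safety primary endpoint, that the overlay is descriptive with no tests, and that details are deferred to the SAP. All of that is true. Thresholding and registration quality control may be specified there; the text available for this review contains no such provision. A descriptive percentage still needs a scale, and the deferral makes the SAP an easy place to add one.

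A second reply is that healthy controls are the reference. They supply a contrast between NASH and control subjects. They do not show what two identically distributed agents would give, because the agents may truly differ in a healthy liver. Section 9.5.3 also tabulates co-location only per subject and overall.

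A third reply is that the percentages depend on assumptions. This stands. Reconstructed, attenuation-corrected SPECT voxels are not independent Poisson counts, and subjects are asked to keep still and breathe shallowly, so registration may be good. Only the direction is firm.

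A reader might infer two stronger claims. One is that the sponsor will report technical discordance as proof that tilmanocept reaches macrophages colloid cannot. Section 1.3 states an expectation, but nothing in the plan commits to that conclusion. The other is that same-agent discordance is an exact null, so that only the excess over it need be interpreted. Step 4 shows that it can err in either direction, and sulfur colloid has no repeat scan.

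**Conclusion.** The point holds as a gap in a secondary, descriptive analysis. As written, Section 9.5.3 would count noise and landmark misregistration as agent-specific binding, and no part of the reviewed text provides a reference for that. The size of the floor cannot be derived from the documents. For noise alone it is roughly 6–59% of positive voxels under the stated assumptions on counts, CV and cut. Shift adds to it by an amount that depends on the assumed texture and displacement. No single percentage should be carried forward as an estimate for this trial. The primary safety endpoint and the sample size are unaffected.

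**What to change.** In Section 9.5.3 or the SAP:

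1. Name the 20-minute tilmanocept scan as the one overlaid on sulfur colloid in the main table, since it is the only time point the agents share.
2. Prespecify one positivity threshold and add a *neither* class.
3. In each subject, apply the same registration and threshold to tilmanocept 20 versus 75 minutes and 20 versus 180 minutes.
4. Report that same-agent discordance, and the measured landmark registration error for every overlay, beside the between-agent table. State that it is an approximate reference and is not to be subtracted.
5. Describe the classes as signal above threshold instead of binding.

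The cost is SAP wording and further runs of the same image-processing steps; no scan, dose or subject is added. The limits should be written into the plan. Same-day repeats may understate Day 0 to Day 3 misregistration, above all for the 20/75 pair. Redistribution may inflate the 20/180 pair. Colloid has no repeat scan. Count levels differ in any 2.5 mCi subjects.

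Excluding a rim of liver should not be part of the main analysis. For a sphere of 1.2–2.0 L (radius 66–78 mm), the volume lost is 1 − ((r − w)/r)³: 18–21% for a 5 mm rim and 34–39% for 10 mm. It also does nothing about misaligned internal texture. If used at all, it should be a sensitivity analysis.

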NASH is an inflammatory syndrome in which immune cells infiltrate into and accumulate in liver tissue [14, 15]. Numerous among these immune cells are macrophages. There are two types of macrophages in the liver. The first type consists of Kupffer cells (aka stellate macrophages) that reside within the endothelial lining of blood vessels in the liver. The second type of macrophages in the liver consists of macrophages differentiated from bone marrow derived monocytes that have infiltrated into the liver and developed into activated macrophages in response to inflammatory signals originating in the liver [14]. It is hypothesized that Tc 99m tilmanocept, through its affinity to CD206, will bind to and accumulate in both types of liver macrophages permitting the degree and anatomical distribution of Tc 99m tilmanocept localization to be used as an indicator of the presence and intensity of NASH related hepatic inflammation. In addition, NASH results in the development of fibrotic lesions in the liver, basically scars resulting from resolved inflammation. These fibrotic lesions are depleted of macrophages, thus are expected to be regions of much reduced Tc 99m tilmanocept localization relative to regions where NASH related inflammation is ongoing [1, 16, 17]. In both cases of either increased Tc 99m tilmanocept localization due to active NASH mediated inflammation or decreased Tc 99m tilmanocept localization due to macrophage depletion due to fibrotic resolution of NASH mediated inflammation, the degree and distribution of Tc 99m tilmanocept localization is expected to significantly differ in NASH involved livers relative to the degree and distribution of Tc 99m tilmanocept localization

observed in livers which are not involved in NASH inflammation. This clinical study will provide a preliminary evaluation of the degree and distribution of Tc 99m tilmanocept localization in healthy livers and those involved in NASH inflammation. If this and follow on studies are successful in establishing that Tc 99m tilmanocept enabled imaging can identify areas of NASH involvement or resolution, then it may be possible to develop Tc 99m tilmanocept as a NASH imaging agent that can assist physicians to non-invasively diagnose and monitor NASH, thus satisfying the need for a non-invasive means to diagnose and assess NASH.

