In addition to the imaging modalities discussed in the previous paragraph, many investigators have evaluated the utility of using various ^{99m}technetium colloids as imaging liver agents [1, 16, 17, 27]. In fact, Tc 99m sulfur colloid will be evaluated as a comparator to Tc 99m tilmanocept for liver imaging in this protocol. Colloids are particles that are actively phagocytized by Kupffer cells. When injected into the blood circulation, Tc 99m sulfur colloid is rapidly cleared from the circulation by the Kupffer cells [26]. Tc 99m sulfur colloid localization to Kupffer cells enables SPECT imaging of livers. Tc 99m tilmanocept localization is expected to differ from Tc 99m sulfur colloid localization in two ways. First, colloidal particles are expected to penetrate poorly into the liver. Thus, Tc 99m sulfur colloid will be unable to localize to aggregates of activated macrophages that have penetrated into liver tissue. Second, Tc 99m sulfur colloid localization to Kupffer cells is independent of their cellular activation state and CD206 expression phenotype. Conversely, Tc 99m tilmanocept localization is CD206 dependent and the extent of localization is expected to vary relative to the level of CD206 expression and the density of CD206 expressing cells.

[figure not shown]

Figure 3. Involvement of the macrophages in the liver damage [15]

Abbreviations: CCL2, CC-chemokine ligand 2; CCR2, CC-chemokine receptor 2; CSF1, macrophage colony-stimulating factor 1; CSF1R, CSF1 receptor; CX3CR1, CX3C-chemokine receptor 1; CXCR, CXC-chemokine receptor; CXCL, CXC-chemokine ligand; DAMPs, damage-associated molecular patterns; FASL, FAS ligand; IL-1β, interleukin-1β; IL-6, interleukin-6; IL-10, interleukin-10; LSEC, liver sinusoidal endothelial cell; LY6C, lymphocyte antigen 6 complex; MoMFs, monocyte-derived macrophages; MSR1, macrophage scavenger receptor 1; NO, nitric oxide; PGE2, prostaglandin E2; ROS, reactive oxygen species; TNF, tumour necrosis factor; VEGFA, vascular endothelial growth factor A.

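### The voxel co-location table has no stated cut-off, no scaling between scans and no 'neither' class, so its shares depend heavily on an unstated choice; a normalised voxel-wise comparison should stand beside it

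*Combined protocol and SAP*

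**What the plan says.** Section 9.5.3 registers the two scans on landmarks, false-colours and overlays them, and labels the voxels: "The resulting voxel colors will be classified as binding tilamanocept, binding sulfur colloid, or binding both". The output is a set of counts: "Frequency tables will created for individual subjects and overall". No intensity threshold is given, no rule puts the two scans on a common scale, and no label exists for a voxel with little of either agent. The same section plans non-parametric density estimates of voxel intensity for each agent, rules out formal hypothesis tests and leaves full detail to the SAP. The third secondary objective (section 2.2) is a comparison of pattern intensity between the agents.

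The background sections say what the scans should show:

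- Tilmanocept "will bind to and accumulate in both types of liver macrophages" (section 1.1), that is, Kupffer cells and infiltrating monocyte-derived macrophages.
- "Colloids are particles that are actively phagocytized by Kupffer cells", and "Tc 99m sulfur colloid localization to Kupffer cells is independent of their cellular activation state and CD206 expression phenotype" (section 1.3).
- For tilmanocept, "the extent of localization is expected to vary relative to the level of CD206 expression and the density of CD206 expressing cells" (section 1.3).
- "Tc 99m sulfur colloid will be unable to localize to aggregates of activated macrophages that have penetrated into liver tissue" (section 1.3).
- On fibrosis: "These fibrotic lesions are depleted of macrophages, thus are expected to be regions of much reduced Tc 99m tilmanocept localization" (section 1.1).

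**The concern.** Two quantitative scans are reduced to a present/absent label for each agent, while the stated mechanism predicts wide overlap in Kupffer cells with graded differences on top. A label of that kind needs a threshold, and a threshold needs a scale shared by both scans. Neither is given. Fibrotic voxels, expected to be low, have no class at all.

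This table is the only planned output that compares the agents voxel by voxel. If its shares move mainly with the colour scale, a reported tilmanocept-only share cannot be read as evidence for or against a different distribution. Nor can it be compared safely between subjects, groups or activity levels.

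**Working it through.** **No plan figure to reproduce.** The protocol gives no cut-off and no expected class share. Section 9.4 gives N=12 without inputs, and no test is planned. The calculations below show sensitivity under assumed inputs.

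**1. Effect of the cut-off when the agents are identical.** Assumed: 200,000 voxels; lognormal true uptake with CV 20%, the same for both agents; independent Poisson counts, mean 50 per voxel; an agent is present if its count exceeds a fraction of that scan's 99.9th percentile. A three-class table reports shares of classified voxels:

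share of classified = (both, as a share of all voxels) / (1 − neither)

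| Cut-off | Both, % of all liver voxels | Neither, % | Both, % of classified voxels |
|---|---|---|---|
| any signal | 100 | 0 | 100 |
| 30% | 95 | 1 | 96 |
| 40% | 70 | 10 | 78 |
| 50% | 35 | 38 | 56 |
| 60% | 13 | 68 | 40 |

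For example, at 50%: 0.35 / (1 − 0.38) = 0.56.

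**2. A real difference.** Tilmanocept is multiplied by 1.5 in 30% of voxels and by 0.5 in 20%. 'Both' is then 71% of classified voxels at the 30% cut-off, 31% at 50%, and 100% if any signal counts. At one fixed cut-off the table separates the scenarios: 96 − 71 = 25 points at 30%, and 56 − 31 = 25 points at 50%. Across cut-offs it does not: 71% with a difference exceeds 56% without one.

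**3. Colloid excluded from some voxels.** A second simulation uses other assumptions: 400,000 voxels, CV 0.3, between-agent correlation 0.5, cut-off as a multiple of mean normal-liver intensity, shares of all voxels. In the exclusion case, 20% of voxels are infiltrated (colloid ×0.1, tilmanocept ×2) and 10% are fibrotic.

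| Cut-off (× mean) | 0.25 | 0.5 | 0.75 | 1.0 | 1.25 | 1.5 |
|---|---|---|---|---|---|---|
| Identical: both, % | 100 | 97.5 | 68.6 | 27.8 | 7.6 | 1.7 |
| Identical: tilmanocept only, % | 0 | 1.1 | 11.3 | 16.5 | 10.7 | 4.6 |
| Exclusion: both, % | 70.1 | 68.3 | 48.0 | 19.4 | 5.3 | 1.2 |
| Exclusion: tilmanocept only, % | 20.0 | 20.8 | 27.9 | 31.3 | 26.0 | 19.2 |

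The tilmanocept-only share is higher under exclusion at every cut-off (19–31% against 0–16.5%). With identical agents and correlation 0 it reaches about 25%, so the ranges overlap unless the cut-off is fixed.

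**4. Aggregates smaller than a voxel.** The documents give neither voxel nor aggregate size. Take 20% of voxels as infiltrated, with no colloid and doubled tilmanocept in the infiltrated part, and count any signal as binding. 'Both' is 100% when the infiltrate fills half of those voxels, 99.8% when it fills 90%, and 80% only when it fills them completely. The SD of the log ratio is 0.50 at half filling and 1.25 at 90%, against 0.21 for identical agents.

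**5. Scaling.** Section 5.2 provides for 8.0 or 2.5 mCi of tilmanocept (2.5/8.0 = 0.31) with a 20% tolerance (6.4 to 9.6 mCi at 8.0, a 1.5-fold span). With a half-life of 6.02 h, 0.5^(t/6.02) leaves 0.962 at 20 min and 0.708 at 180 min. If the cut-off were on raw counts at equal acquisition time (0.5 × mean, identical uptake as in step 3), going from 8.0 to 2.5 mCi would move 'both' from 97.5% to 4.0% and colloid-only from 1.1% to 94.6%.

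**6. A measure without a cut-off.** Divide each voxel by its scan's liver mean and take the log ratio of tilmanocept to sulfur colloid. With m counts per voxel in each scan, counting noise alone gives an SD of about √(2/m): √(2/50) = 0.20 and √(2/20) = 0.32. Simulated values for identical agents are 0.21 and 0.33. With the difference of step 2 they are 0.44 and 0.51.

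**The case against.** The strongest reply has four parts.

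- **The classes have a biological basis.** Section 1.3 names two expected differences between the agents. The first is one of kind: no colloid in infiltrated aggregates. A tilmanocept-only class is a direct readout of that. This stands. A reader might infer that the agents differ only in degree and that the class is meaningless, but section 1.3 does not support that.
- **The shares respond to the agents.** Steps 2 and 3 show separation at any fixed cut-off. This also stands. A reader might infer that the shares reflect the colour cut-off instead of the agents; they reflect both.
- **Graded analyses are already planned.** Section 9.5.3 has the density estimates, and the synopsis adds descriptive statistics of localization intensity by time point, compared with controls. So the table does not carry the third secondary objective alone, and graded information is not lost from the plan. But separate densities for each agent cannot show whether a voxel high for one agent is low for the other.
- **Detail is deferred.** The SAP, or Figure 7, which was not visible in the text reviewed, may define the colour mapping. No SAP text on this appears in the document, and the three-class structure is already set in section 9.5.3.

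The alternative is not free of choices either: ratio multiples are cut-offs too, and the log ratio contains counting noise. In a descriptive Phase 1 study of at most 12 subjects without tests, this is a matter of interpretability, not of error rates.

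**Conclusion.** The concern holds in a limited form. The three-class shares carry information about the agents, but they cannot be interpreted until the cut-off, the scale and the treatment of low-signal voxels are stated. With identical agents, the cut-off alone moves 'both' from 96% to 40% of classified voxels (95% to 13% of all liver voxels), and from 100% to 1.7% of all voxels under the second set of assumptions. If any signal counts as binding, the table stays at or near 100% 'both' unless colloid is wholly excluded from a voxel.

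These sizes rest on assumed CV, counts, correlation and uptake patterns; only the activities, tolerance, imaging times and half-life come from the protocol. The direction does not depend on the exact values. The change should be made, because this is the only voxel-paired output for a secondary objective about pattern intensity and the remedy uses the same images.

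**What to change.** In section 9.5.3 and the SAP:

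1. Divide each liver voxel by that scan's whole-liver mean.
2. Alongside the class table, report for each subject the voxel rank correlation, the SD of the log ratio of tilmanocept to sulfur colloid, and the share of liver volume above and below pre-stated ratio multiples. Count zero-colloid voxels as above; do not drop them. When they were dropped in a trial run, complete exclusion gave an SD of 0.21, the same as no difference.
3. Summarise the per-subject values by NASH and control and by tilmanocept activity group.
4. If the table is kept, use one pre-stated cut-off on the normalised scale for all subjects, add a 'neither' class, and show the shares over a range of cut-offs.

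The cost is wording and a little programming; images and registration are unchanged. There are two limits. Normalising removes the overall uptake level, so total liver uptake (section 9.3) must still be reported separately. The log ratio also needs a common light smoothing or a minimum-count rule. At equal acquisition time and uptake, 50 counts at 8.0 mCi become 50 × 2.5/8.0 = 15.6 at 2.5 mCi. Against a 50-count colloid scan the noise SD is then about √(1/15.6 + 1/50) = 0.29 instead of 0.20, so the activity groups should not be pooled on this measure.
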